11.2 METHOD OF SUMMARIZATION AND ANALYSIS

11.2.1 ADVERSE EVENTS DURING CHEMORADIATION

Each participating institution coded adverse events with their preferred term and organ class using MedDRA system organ class. Whether or not the adverse event was related to BMX-001 was determined for each event.

The initial summary of adverse events will consider all Treatment Emergent AE (TEAE) occurring during chemoradiation regardless of attribution to BMX-001. A TEAE is an event emerging during treatment having been absent pre-treatment or having worsened relative to pre-treatment. The period of observation that will be the focus of this tabulation will extend 2 weeks after termination of radiation treatment.

The population for these summaries will be the safety population as defined in Section 6.

For each study arm, the number of subjects with at minimum one Treatment Emergent AE (TEAE) will be tabulated by preferred term and MedDRA system organ class. Subjects with more than one TEAE will be counted only once, at casualty, for each system organ class /preferred term. Multiple TEAEs in a subject will be counted once per system organ class and preferred term. Summaries will be sorted by system organ class and decreasing total incidence of preferred term.

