### Additional possible side effects:

- Light-activated skin rash in response to sun exposure (not yet reported in humans)
- Red to dark color of urine (not yet reported in humans)
- It is also possible that previously unobserved and unexpected side effects could occur.

Human safety data for BMX-001 in combination with TMZ and RT has been studied in Phase 1 of this clinical trial. BMX-001 at 42 mg/subject loading dose and 20 mg/subject subsequent doses given twice weekly was the maximum administered dose and 28 mg/subject loading dose and 14 mg /subject for subsequent twice weekly doses was the MTD. Sinus tachycardia (grade 3) was the dose-limiting toxicity at 42 mg/subject loading dose (n=1). The only other related grade  $\geq$  3 event seen was hypotension (grade 3) (n=1). The most common related toxicity was grade 1 injection site reaction (n=7). There is no apparent toxicity to end organ tissues or bone marrow.

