b Will transition to 5-day TMZ dosed at 150-200 mg/m^2 po daily for the 1st 5 days in 28-day cycle (Adjuvant Phase). Study assessments for HRQoL Measurements, and Hair Loss Evaluation will be obtained approximately every 8 weeks (+/- 2 weeks) when a subject returns for a Standard of Care visit, until tumor progression, death, or patient comes off of study. Cognitive testing will also be completed every 8 weeks and at SOC visits; Cognitive testing will continue after tumor progression. CBC with differential will be obtained approximately on Days 21 or 28 of each 28-day cycle, and CMP will be obtained approximately on Day 21 of each 28-day cycle, or per the ordering physicians Standard of care practice, during the adjuvant phase, until the subject comes off the study. If subject is transitioned to metronomic temozolomide because of poor tolerance to 5-day temozolomide, then they will continue to be on study. Moreover, if Optune is used during the adjuvant phase, then they will continue to be on study. Adjuvant temozolomide can start up to 4 weeks after radiation therapy has completed.

c Starting at Loading dose day or Day -5 to 0, this will occur once every other week during weeks 1-8. This may be modified to meet standard of care scheduling for patient visits.

d Weekly CBCs and CMPs will begin at week 2 and continue through week 8. Platelet count is part of CBC with differential count.

e ECG will be done at screening for all subjects. For subjects in Arm A, ECG will also be obtained before the loading dose is administered (within 5 to 60 minutes before the dose), and at 60 (+/- 15 min) minutes after the loading dose. Pre-dose (within 5 to 60 minutes before the dose), and Post-dose ( 60 +/- 15 min) ECGs will also be collected at the Week 1 first maintenance dose and on either one of the BMX-001 injection days in Week 4.

f See Appendix B for timing of PK sampling, Day 8 and Day 36 only. Phase 1- all subjects, Phase 2- 6 subjects at Duke. g HRQoL measurements will be completed during Screening as a baseline and then approximately every 8 weeks when a subject returns for a Standard of Care visit during the Adjuvant Phase. These assessments should be completed prior to other study-related evaluations at study visits, if at all possible.

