h DTI/Susceptibility Imaging is for clinical centers selected by the sponsor and completed at baseline, during the Adjuvant Phase before the start of the first cycle of adjuvant temozolomide, as well as 6 months (approximately 24 weeks, +/- 2 weeks) after radiotherapy/chemotherapy

i Toxicity assessment will continue to be obtained at every SOC clinic visit during the Adjuvant Phase for a minimum of 30 days after last BMX-001 treatment for subjects receiving BMX-001 or last chemo/RT for subjects not receiving BMX-001, and also followed for any unresolved adverse events considered related to study therapy.

j For BMX-001, this dose will be the loading dose. In Phase 2- Applicable only for patients in Arm A.

k For BMX-001, doses (50% of the loading dose) will be twice a week subcutaneously weeks 1-8. There will only be two doses per week regardless of being a loading or maintenance dose. In Phase 2- Applicable only for patients in Arm A. I For patients in Phase 2 Arm B (standard RT + TMZ without BMX-001), vital sign evaluation will only be required on days of the History and Physical assessment.

m Arm A: Patients will be monitored at drug administration with vital signs and injection site reaction at pre dose, at 5 (+/-2), 15 (+/-3), 30 (+/-5), and 60 (+/-5) minutes post administration on the BMX-001 loading dose. Patients will be monitored at drug administration with vital signs and injection site reaction at pre dose, at 5 (+/-2), 15 (+/-3) and 30 (+/-5) minutes post administration on BMX-001 maintenance injection days. See Section 0.

o Phase 2 only, subjects will be randomized after all eligibility criteria is confirmed.

p For Phase 2: For subjects in Arm A, this column is the day of the BMX-001 Loading Dose. For Subjects in Arm B, these items should occur -5 to 0 days prior to the start of RT. The procedures for this visit should not take place until final eligibility is confirmed and randomization has occurred.

q In Phase 2, subjects randomized to Arm B will NOT have a Week 7 or Week 8 research study visit.

r In Phase 2, subjects randomized to Arm B do not have a Week 1 study visit, although they will be in the clinic for the start of RT and TMZ.

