11.1 ENDPOINTS

The phase 2 portion of this study has two adverse event endpoints:

(1) The proportion of patients who experience any grade 3 or 4 adverse event during radiation and temozolomide treatment, and

(2) The proportion of patients who experience a grade 3 or 4 adverse event that is definitely, possibly, or probably related to BMX-001 treatment during this same period.

Adverse events occurring between baseline through 2 weeks after discontinuation of radiation will be the focus of these analyses and will be summarized.

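### The SAP tabulates adverse events by arm with no allowance for scheduled ECGs after screening in Arm A only and far more frequent vital signs in Arm A

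*SAP*

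**What the plan says.** The third Phase 2 secondary objective compares safety and tolerability between arms. SAP 11.2.1 covers all treatment-emergent events through 2 weeks after radiation, irrespective of attribution to BMX-001: "For each study arm, the number of subjects with at minimum one Treatment Emergent AE (TEAE) will be tabulated by preferred term and MedDRA system" (that is, by organ class). The first endpoint in SAP 11.1 is "The proportion of patients who experience any grade 3 or 4 adverse event during radiation and temozolomide treatment".

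The schedule that feeds these tables is in Protocol Section 13, Table 4 and its footnotes:

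- **ECG, both arms (footnote e):** "ECG will be done at screening for all subjects".
- **ECG, Arm A only (footnote e):** "For subjects in Arm A, ECG will also be obtained before the loading dose is administered", and again 60 minutes after it. Pre- and post-dose "ECGs will also be collected at the Week 1 first maintenance dose and on either one of the BMX-001 injection days in Week 4".
- **Vital signs, Arm A (footnote m, Section 9.1.3):** heart rate, blood pressure and oxygen saturation before each injection and at 5, 15 and 30 minutes after it, plus 60 minutes on the loading day. Injection sites are checked at the same times.
- **Vital signs, Arm B (footnote l):** "vital sign evaluation will only be required on days of the History and Physical assessment". Table 4 places those days at Day -5 to 0 and every other week. Footnotes q and r remove the Arm B study visits in weeks 1, 7 and 8.

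SAP 11.2.3 tabulates BMX-001-related events for Arm A alone, SAP 11.2.4 summarises vital signs before and after injection, and SAP 19 lists abnormal ECGs after BMX-001. The SAP gives no caveat, common-schedule table or sensitivity analysis for unequal monitoring.

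**The concern.** Under Protocol 14 and 14.1, adverse events include unfavourable signs and abnormal findings, and are identified partly from study assessments. More measurement can therefore produce more recorded events. Tachycardia, a blood pressure change, desaturation or a long QTc may arise from disease, steroids, anti-emetics or chemoradiation. Such a finding has many more chances of being seen in Arm A.

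These are also the terms of most interest for this drug. Protocol 5.6.2 names tachycardia, hypotension and QTc prolongation as possible effects, and both related grade 3 or higher events in Phase 1 were sinus tachycardia and hypotension. In the full table, an Arm A excess in these terms could be read as toxicity when part of it is detection, and the reader has no display that helps to separate the two.

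**Working it through.** The plan states no sample size, power or error rate for the adverse event comparison, so there is no figure to reproduce. The check is a count of scheduled assessments, then an illustration.

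**ECGs after screening** (footnote e, Section 13.8.3)

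- Arm A: 3 days x 2 tracings = 6. One precedes any BMX-001. The loading-day pair falls at or just before the start of chemoradiation, so 4 come after the loading day.
- Arm B: 0.

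**Vital signs through week 6**

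- Arm A dosing days: 1 loading + 6 weeks x 2 = 13, in line with the 6 weeks or 13 doses in the SAP 6 definition of the Treated Population.
- Arm A sets of readings: 5 on the loading day + 12 x 4 = 53.
- Arm B days: Day -5 to 0 and weeks 2, 4 and 6 = 4. The loading day is counted in Arm A, so the matching Day -5 to 0 visit must be counted in Arm B.
- Arm A days without an Arm B counterpart: 13 - 4 = 9, and 9/13 = 69%. This assumes that history-and-physical days in Arm A coincide with dosing days.
- Over all 17 planned doses (Section 9.1.5): 5 + 16 x 4 = 69 sets on 17 days, still against about 4 days in Arm B.

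**Illustration with no drug effect.** Let p be the chance, equal in both arms, that a monitored day yields a recordable vital-sign event, with independent days and nothing noticed on other days. The share of patients with at least one event after k days is 1 - (1 - p)^k. The values of p are assumptions; the documents give none.

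| p per day | Arm A, k = 13 | Arm B, k = 4 | Gap (points) |
|---|---|---|---|
| 0.5% | 6.3% | 2.0% | 4.3 |
| 1% | 12.2% | 3.9% | 8.3 |
| 2% | 23.1% | 7.8% | 15.3 |

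With the 78 and 71 treated patients of SAP 10.3.2, the 1% row is about 10 patients (78 x 0.122) against 3 (71 x 0.039).

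For ECG findings, an assumed 1%, 2% or 5% chance per tracing over the 5 tracings after the first dose gives 4.9%, 9.6% or 22.6% in Arm A. By schedule, none could be found in Arm B.

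**Two schedule points bear on the count.** Table 4 and footnote c schedule examinations every other week, while Section 13.8.2 says they may be done every two weeks during chemoradiation. If Arm B had only 1 such day, its 1% figure falls to 1.0% and the gap becomes 12.2 - 1.0 = 11.2 points. Section 13.8.2 also omits oxygen saturation from its list of vital signs, so Arm B may have few or no saturation readings.

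**The case against.** **Most of the table is not affected.** Both arms have adverse event inquiry at each study visit. Footnote d sets weekly blood counts and chemistry with no arm restriction. Fatigue, nausea, cytopenia and chemistry rows do not depend on monitoring after injection. This stands. A reader might infer that the by-arm tables as a whole compare events looked for in one arm only. The schedule supports that only for ECG-detected findings and injection-site reactions; for heart rate and blood pressure the difference is one of intensity.

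**No between-arm test is planned.** SAP 11.1 and 11.2 describe summaries and tabulations. This stands too. A reader might infer a high chance of a falsely significant safety difference, but no planned analysis has such an error rate. Only the gap in percentages is relevant.

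**The illustration may overstate the gap.** Patients attend radiation five days a week under close follow-up (Protocol 9.1.8), and SAP 11.2.4 lists only clinically significant vital signs. Events can surface between scheduled readings, and a passing abnormal value need not become an event. This is fair, and is why the figures are illustrative.

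**Expected side-effect rates do not size the bias.** Protocol 5.6.2 expects transient tachycardia in more than 30% of subjects, but as an effect of BMX-001. It says nothing about background events missed in Arm B.

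**Existing outputs cover it.** They do so only in part. The Arm A displays in SAP 11.2.3, 11.2.4 and 19 describe Arm A; none changes the by-arm comparison in 11.2.1.

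**Conclusion.** The point holds in a limited form. The schedule differs as counted, and SAP 11.2.1 compares arms across that difference without saying so. The bias falls mainly on ECG and QTc, heart-rate, blood-pressure and oxygen-saturation terms, their system organ classes, and any count of patients with at least one event.

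Its size cannot be derived from the documents. About 4 to 15 points is what 13 against 4 monitored days would give at assumed daily rates of 0.5% to 2%, with no drug effect and no detection on other days.

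A reader might also infer that the grade 3-4 endpoint is seriously compromised. The documents do not support that. Reported QT prolongation did not exceed grade 2 (Protocol 9.1.4). The grade 3 tachycardia in Phase 1 was at a loading dose of 42 mg, not the Phase 2 dose, and Section 9.1.3 reports no hypotension at the Phase 2 dose. The effect there is probably small, though not shown to be zero.

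The closer monitoring of Arm A is not itself the fault; the gap is in the analysis plan.

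**What to change.** In SAP 11.2.1:

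1. Keep the full by-arm tables as the main safety display.
2. Add a supplementary by-arm version that leaves out, in both arms, what only Arm A procedures can yield: ECG-detected findings and injection-site reactions. Show those for Arm A alone.
3. For vital signs, compare arms only on history-and-physical-day readings, using the pre-dose reading in Arm A, and report pre- to post-dose changes within Arm A. If Arm B has no oxygen saturation readings, say that this comparison cannot be made.
4. Do not remove symptomatic, treated, serious or grade 3-4 events because they began on a dosing day. Such a rule would strip real post-dose events from Arm A while keeping every Arm B event.
5. State that by-arm differences in ECG and vital-sign terms in the full table partly reflect unequal monitoring, and that cardiovascular conclusions do not rest on the supplementary version alone.

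Table 4 with footnote c and Section 13.8.2 must be reconciled on examinations during chemoradiation, so that the Arm B vital-sign days are known.

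The cost is SAP wording and one extra set of tables from data already collected, with no new visits or procedures. The drawback is that the supplementary version omits some real drug effects, so it must sit beside the full table and never replace it.

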### 5.6.2 Risks of BMX-001

Studies have been performed using intravenous infusions of a related metalloporphyrin in multiple models including rats, mice, dogs, guinea pigs, and baboons with the finding of dose-related hypotension [2]. Metalloporphyrin compounds being evaluated are potent, catalytic antioxidants and have the potential to scavenge superoxide within the vascular system and thereby change the balance of superoxide and nitric oxide in the microvasculature. This would augment the vasodilating activity of nitric oxide and lead to hypotension [2]. This has been found in animal models to be a significant, but transient side effect and therefore blood pressure monitoring is essential in this clinical trial of a metalloporphyrin compound. Studies of rats, mice, and monkeys have been performed with BMX-001 and have shown transient, dose-related hypotension. Hypotension is related to plasma Cmax levels and subcutaneous administration significantly reduces the risk of this toxicity in mice and primates (unpublished data per BioMimetix JV, LLC). This hypotensive effect was also found in primates. We have designed this protocol to monitor blood pressure closely.

A summary of the possible adverse side effects that could be associated with BMX-001 administration is below. These possible side effects are dose-dependent, and the relatively low doses of this drug planned in this study have not been associated with side effects in animals other than those related to the color of the injected drug.

The most common side effects (expected to occur in more than 30% of subjects) are:

- Red to brown discoloration of the skin at the injection site which may take up to several weeks to resolve
- Irritation at the site of the injection of the drug under the skin
- Transient tachycardia from study drug

Less common side effects (expected to occur in 10-30% of subjects) are:

- Transient pain at the injection site. This is expected to be related to the concentration of administered drug and the volume administered, rather than subject body size
- Local histamine release which could be caused by study drug. This could cause pruritus (itching), erythema (redness), edema (swelling), urticaria (welts). This is expected to resolve within a couple of hours of injection

Rare side effects (expected to occur in less than 10% of subjects) are:

- Temporary hypotension (low blood pressure)
- Malaise or "not feeling well" for a few hours
- Prolongation of the QTc interval

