#### 16.5.2.3 Secondary Objective #3 for Phase 2: Adverse Events

The phase 2 portion of this study has two adverse event endpoints: (1) The proportion of patients who experience any grade 3 or 4 adverse event during radiation and temozolomide treatment, and (2) The proportion of patients who experience a grade 3 or 4 adverse event that is definitely, possibly, or probably related to BMX-001 treatment during this same period. Adverse events occurring between baseline through 2 weeks after discontinuation of radiation will be the focus of these analyses.

Adverse Event Monitoring and Tabulations: Adverse events will be tabulated in a different manner for semi-annual reports to the DSMB-Plus / DSMB, the manuscript summarizing the results of this study, and the final report included within ClinicalTrials.gov.

*DSMB-Plus / DSMB Monitoring:* Two tabulations of adverse events occurring during concurrent chemoradiation will be generated for DSMB-Plus / DSMB review including one that includes all toxicities regardless of attribution, and another that includes only toxicities that are possibly, probably, and definitely related to BMX-001 treatment. For each of these tabulations, the maximum grade of each type of toxicity experienced by each patient will be summarized with frequency distributions within each treatment group. The period of observation that will be the focus of these tabulations will extend 2 weeks after termination of radiation treatment. Additional tabulations will summarize adverse events experienced during adjuvant treatment.

For the manuscript, similar summaries of adverse events will be generated.

For ClinicalTrials.gov, serious adverse events and other adverse events will be summarized separately. These tabulations will reflect the number of patients who experience each type of toxicity regardless of grade or attribution.

16.5.2.4 **Secondary Objective #4 for Phase 2: Progression-Free Survival** Progression-Free Survival (PFS) is defined as the time between initiation of protocol treatment and disease progression or death. If the patient remains alive without disease progression, then PFS will be censored at last follow-up. Analyses similar to those described for OS will be generated for PFS.

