3 INTRODUCTION

This Statistical Analysis Plan (SAP) is based on the current trial protocol (version 9.0 dated 25 May 2019). If statistical methods differ substantially between the SAP and the protocol, refer to the SAP.

The SAP describes the datasets and the statistical methods to be used for reporting and analysis of all data collected during the trial.

If a future protocol amendment necessitates a substantial change to the statistical analysis of the trial data, the SAP will be amended. If, after the database is locked, additional analyses are required to supplement the planned analyses described in this SAP, those unplanned analyses will not be described in an amended SAP, but they will be identified in the final Clinical Study Report (CSR).

We have considered the following guidelines when writing this SAP:

- International Conference on Harmonization (ICH) E9, Guidance for Industry: Statistical Principles for Clinical Trials
- ICH E3, Guidance for Industry: Structure and Content of Clinical Study Reports.

Statistical analysis will primarily be conducted using SAS version 9.4, with additional analyses and data visualization performed using the R software (version 4.2.1 or later).

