11.2.3 ADVERSE EVENTS DURING CHEMORADIATION ATTRIBUTABLE TO BMX-001

Given that this is an open-label treatment study, adverse events attributable to BMX-001 will only occur in patients within Arm A who receive BMX-001.

For Arm A, the number of subjects with at least one BMX-001 related Treatment Emergent AE (TEAE) will be tabulated by preferred term and MedDRA system organ class. Subjects with more than one BMX-001 related TEAE will be counted only once, at casualty, for each system organ class /preferred term. Multiple TEAEs in a subject will be counted once per system organ class and preferred term. This summary will be sorted by system organ class and decreasing total incidence of preferred term.

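### The SAP's adverse event tables count patients by term without grade, dropping the protocol's maximum-grade tables and leaving the SAP's own grade 3–4 endpoints without a table

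*SAP*

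**What the plan says.** **Protocol 16.5.2.3** plans two Phase 2 tabulations for the DSMB-Plus/DSMB, one of all toxicities and one of those related to BMX-001. In each, "the maximum grade of each type of toxicity experienced by each patient will be summarized with frequency distributions within each treatment group". The manuscript is to receive similar summaries. Only the ClinicalTrials.gov tables are meant to ignore grade.

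**SAP 11.2.1**, for all TEAEs in each arm: "the number of subjects with at minimum one Treatment Emergent AE (TEAE) will be tabulated by preferred term and MedDRA system organ class". For repeat events: "Subjects with more than one TEAE will be counted only once, at casualty, for each system organ class /preferred term".

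**SAP 11.2.3**, on the Arm A events attributed to BMX-001, says this: "the number of subjects with at least one BMX-001 related Treatment Emergent AE (TEAE) will be tabulated by preferred term and MedDRA system organ class". Its rule for repeat events is this: "Multiple TEAEs in a subject will be counted once per system organ class and preferred term".

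**SAP 11.1** keeps two endpoints: the proportion of patients with any grade 3 or 4 event, and the proportion with a grade 3 or 4 event related to BMX-001.

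**SAP 19** lists summaries of AEs, TEAEs, BMX-001-related TEAEs and SAEs. None is described as graded, and none is assigned to the 11.1 endpoints.

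**SAP 3**: "If statistical methods differ substantially between the SAP and the protocol, refer to the SAP".

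**The concern.** The third secondary objective is comparative tolerability. For this drug, much of the clinical meaning lies in the grade:

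- Protocol 5.6.2 puts "Transient tachycardia from study drug" among the effects expected in more than 30% of subjects. The same section reports grade 3 sinus tachycardia as the Phase 1 dose-limiting toxicity (one patient, 42 mg loading dose).
- The criteria for holding BMX-001 in protocol 13.4.1 are themselves graded. They include QTc prolongation from grade 2 and intolerable injection-site reactions from grade 2.
- Protocol 9.1.4 reports that the QT prolongations seen after the 28 mg loading dose did not exceed grade 2.

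A table that counts a patient once per term, whatever the grade, merges these cases. A programmer who follows the SAP would give the study report the grade-free format that the protocol reserves for the registry.

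**Working it through.** The plan states no figure to reproduce. The check is a comparison of texts, followed by a short illustration.

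**1. What each planned output shows**

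| Output | By term? | By grade? |
|---|---|---|
| Protocol 16.5.2.3, board and (similar) manuscript tables | yes | yes, maximum grade |
| SAP 11.2.1, all TEAEs, by arm | yes | no |
| SAP 11.2.3, related TEAEs, Arm A | yes | no |
| SAP 11.1, endpoints 1 and 2 | no, all terms pooled | grade 3–4 only; no method in 11.2, no table in 19 |
| SAP 10, thrombocytopenia | one term | grade 3–4 |
| SAP 11.2.2, SAE summary and narratives | yes | selected by seriousness, not grade |
| SAP 11.2.4, AE listing | patient level | columns not specified |

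Only the protocol's tables cross term with grade for all toxicities, and the SAP does not carry them over. In the SAP, thrombocytopenia is the only toxicity for which a summary shows grade 3–4 by term.

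**2. Grade 2 against grade 1.** The 11.1 endpoints start at grade 3 and the term tables have no grade. Grade 2 QTc prolongation and grade 2 injection-site reactions are therefore missed by the endpoints and merged with grade 1 in the tables.

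**3. The counting rule.** The words *at casualty* in SAP 11.2.1 and 11.2.3 have no defined meaning. They do not say that the highest grade is the one counted.

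**4. Illustration with tachycardia.** Inputs: more than 30% expected (protocol 5.6.2) and 78 Arm A patients who received protocol treatment (SAP 10.3.2).

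0.30 × 78 = 23.4, so more than 30% means at least 24 patients.

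The documents give no grade 3 tachycardia rate at the Phase 2 dose, so the rates p below are assumptions. Expected count = 78p; chance of at least one = 1 − (1 − p)^78.

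| Assumed p | Expected grade 3 patients | Chance of at least one |
|---|---|---|
| 1% | 0.8 | 54% |
| 3% | 2.3 | 91% |
| 5% | 3.9 | 98% |
| 10% | 7.8 | over 99% |

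With 24 patients affected, the SAP's tachycardia row reads 24/78 in every case.

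**The case against.** The other side has several good points.

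- **The SAP is not blind to grade.** Endpoint 2 is restricted to BMX-001-related grade 3–4 events, so it separates them from TMZ and radiation toxicity. If several tachycardias were grade 3 and attributed to the drug, this proportion would rise. That stands, but the endpoint does not say which term was responsible, and it has no table.
- **Other outputs help.** All AEs are listed and SAEs have narratives. Clinically significant vital signs around injection are summarized, and abnormal ECG findings are listed. A reader might infer that severe events could not be identified anywhere, and the documents do not support that. These outputs still do not summarize grade by term and arm, and a grade 3 event need not be serious.
- **The protocol's maximum-grade rule is written for board reports.** It reaches the manuscript only through similar summaries. SAP 11.2.1 also calls its table the initial summary, so the SAP's silence need not mean replacement. That is fair, but neither SAP 11.2 nor section 19 names a graded table, and the SAP governs where methods differ substantially.
- **The phrase *at casualty* could be a slip for something else**, such as causality. The supportable request is for an explicit rule; maximum grade is the one that agrees with protocol 16.5.2.3.

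Three further inferences are tempting but fail. Grade 3 hypotension is not hidden among tachycardia counts. It is a separate term, expected in under 10%, was not named as the dose-limiting toxicity, and was not seen in Phase 1 at the Phase 2 dose. The protocol calls the expected tachycardia transient; it does not call it mild or benign. Nor does the gap justify arm-difference intervals for drug-specific events. BMX-001-related events and injection-site reactions can occur only in Arm A. Post-dose vital signs and on-treatment ECGs are also planned only there (protocol 9.1.3, 13.8.3 and the notes to Table 4), so arm contrasts for tachycardia, hypotension and QTc would partly reflect unequal detection.

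**Conclusion.** The point holds for the summary tables. SAP 11.2.1, 11.2.3 and 19 omit grade, the protocol's maximum-grade tabulations are not carried into the governing document, and the two 11.1 endpoints have no specified output. Apart from thrombocytopenia, the planned tables cannot show which terms reached grade 3–4. For no term can they separate grade 1 from grade 2.

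The 24 of 78 is an illustration. It applies a risk-section expectation to a provisional count of treated patients, and the grade 3 rates are assumed. The conclusion depends on none of these numbers, because the row is the same for any split of grades.

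The primary survival analysis is unaffected. This is a reporting defect in a secondary objective that should be corrected before the tables are programmed.

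**What to change.** 1. In SAP 11.2.1, 11.2.3 and 19, count each subject once per preferred term at the maximum CTCAE grade, with separate columns for grades 1, 2, 3, 4 and 5. Show all TEAEs by arm and BMX-001-related TEAEs for Arm A only.
2. Add a table to section 19 for the two 11.1 endpoints: endpoint 1 by arm, endpoint 2 as an Arm A proportion with an exact binomial interval.
3. Replace *at casualty* in 11.2.1 and 11.2.3 with an explicit rule consistent with protocol 16.5.2.3, namely the highest grade.
4. Do not add arm-difference intervals for BMX-001-related events, injection-site reactions, QTc prolongation, tachycardia or hypotension. Note under the tables that Arm A is monitored more intensively.

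The cost is SAP wording and table shells. Protocol 14.1 already has adverse events graded by CTCAE 4.03, so no new data are needed, and no dose or treatment rule is touched.
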